**6.1 Study Intervention(s) Administration**

The actual dose to be administered will be based on measured body weight. A table will be included in the Pharmacy Manual.

|  |   |   |
|--|---|---|
|  | 
Treatment group 1a: S. mansoni-infected children, 4 to 6 years of age.
 
Cohort 2: S. mansoni-infected children, 2 to 3 years of age.
 
Cohort 3: S. mansoni-infected children, 3 to < 24 months of age.
 
Cohort 4: S. haematobium-infected children, 3 months to 6 years of age.
 | 
Treatment group 1b: S. mansoni-infected children, 4 to 6 years of age
 |
| Study Intervention Name:                | L-PZQ ODT   | Commercial PZQ (Biltricide®)  |
| Dose Formulation:                       | 150 mg tablet   | 600 mg tablet   |
| Unit Dose Strength(s)/ Dosage Level(s): | L-PZQ ODT at 50 mg/kg
For Cohort 4, the dose might be increased to 60 mg/kg after IDMC review  | Biltricide at 40 mg/kg  |
| Route of Administration:                | Oral  | Oral  |

|                                |   |  |
|--------------------------------|---|--|
| Dosing Instructions:    | Single dose of L-PZQ ODT, dispersed in water, after food intake (see Section 6.6, Dose Selection and Modification)  | Single dose of commercial PZQ (Biltricide).
The Biltricide tablets will be divided into 150 mg parts, crushed, suspended in water, and administered after food intake.  |
| Supplier/Manufacturer:  | Farmanguinhos Fiocruz, Brazil   | Merck KGaA (commercial product sourced from Bayer Germany)   |
| Packaging and Labeling: | L-PZQ ODT tablets will be supplied by the sponsor in CCI [REDACTED]
[REDACTED]
[REDACTED]. Each CCI [REDACTED] contains 150 tablets.

Each CCI [REDACTED] will be packaged and labeled per all applicable regulatory requirements and Good Manufacturing Practice Guidelines. | Biltricide comes in a CCI [REDACTED] with white closure, containing 6 tablets. CCI [REDACTED]

Each CCI [REDACTED] will be packaged and labeled per all applicable regulatory requirements and Good Manufacturing Practice Guidelines. |

## 6.2 Study Intervention(s) Preparation, Handling, Storage, and Accountability

The Investigator and/or designee is responsible for Study Intervention accountability, reconciliation, and record maintenance (i.e., receipt, reconciliation, and final disposition records).

- Upon receipt of the Study Intervention(s), the Investigator or designee must confirm appropriate temperature conditions have been maintained during transit and any discrepancies are reported and resolved before use. Also, the responsible person will check for accurate delivery and acknowledge receipt by signing or initialing and dating the appropriate document and returning it to the location specified. A copy will be archived for the Investigator Site File.
- Only participants enrolled in the study may receive Study Intervention(s) and only authorized site staff may supply or administer it. All Study Intervention(s) must be stored in a secure environmentally-controlled, and monitored (manual or automated) area, in accordance with the labeled storage conditions (L-PZQ ODT: CCI [REDACTED], and with access limited to the Investigator and authorized site staff).
- The investigator and/or designee is responsible for ensuring that the temperature at which the Study Intervention is to be stored is monitored throughout the duration of the study and that temperature records are maintained. The temperature will be recorded continuously and monitored manually twice a day.

- Dispensing will be recorded on the appropriate accountability forms so that accurate records will be available for verification at each monitoring visit.
- The preparation of the number of tablets for the individual subject in each cohort will be done by a pharmacist and pharmacist assistant under the responsibility of the Investigator. The pharmacy will prepare the Study Intervention for all participants per cohort according to the treatment randomization list when applicable (Treatment groups 1a and 1b) and the measured body weight in accordance with standard procedures.
- Biltricide tablets will be divided into 150 mg parts, crushed and suspended in water. L-PZQ ODT tablets will be dispersed in water. Study Interventions will be administered within one hour after food (details described in the corresponding informed consent forms) intake. Detailed procedures are described in the Pharmacy Manual.
- Study Intervention(s) accountability records at the study site will include the following:
  - Confirmation of receipt, in good condition and in the defined temperature range.
  - The inventory provided for the clinical study and prepared at site.
  - The dose(s) each participant used during the study.
  - The disposition (including return, if applicable) of any unused Study Intervention(s).
  - Dates, quantities, batch numbers, vial numbers, expiry dates, formulation (for Study Interventions prepared at the site), and the participant numbers.
- The Investigator site will maintain records, which adequately documents that participants were provided the doses specified in this protocol, and all Study Intervention(s) provided were fully reconciled.
- Unused Study Intervention(s) must not be discarded or used for any purpose other than the present study. No Study Intervention that is dispensed to a participant may be re dispensed to a different participant.
- A Study Monitor will periodically collect the Study Intervention(s) accountability forms.
- Further guidance and information for the final disposition of unused Study Intervention(s) are provided in the Pharmacy Manual.

### **6.3 Measures to Minimize Bias: Study Intervention Assignment and Blinding**

#### **6.3.1 Study Intervention Assignment**

The study consists of 4 cohorts, which will be enrolled in parallel. Cohort 1 includes a 2:1 randomization of children 4 to 6 years of age infected with *S. mansoni* to a single dose of the L-PZQ ODT 50 mg/kg (test arm; Treatment group 1a) or a single dose of the PZQ standard of care (rac-PZQ crushed tablets 40 mg/kg; Treatment group 1b). No randomization is foreseen for Cohorts 2, 3, and 4.

The participants in Cohort 1 will be stratified according to their infection intensity, with target enrollment of 40% moderate/heavy infections and 60% light infections. No stratification will be

implemented for Cohorts 2, 3, and 4. No stratification will be implemented per sex or per country.

In Treatment Groups 1a and 1b only, after confirmation of participant's eligibility and at the last practical moment prior to study intervention administration, participants will be centrally allocated to either L-PZQ ODT or Biltricide in a 2:1 ratio using a computer-generated randomization list integrated in the electronic data capturing system. Randomization will not be used to allocate participants in any of the other cohorts.

Before the study is initiated, the login information and directions for the electronic data capturing system will be provided to each site. The site will capture the participant's data in the electronic data capturing system and by completing the corresponding forms receive the study intervention group for participants of Cohort 1.

### **6.3.2 Blinding**

#### **Blinding Method**

This is an open-label study in which participants will receive a single treatment dose of the L-PZQ ODT formulation (Treatment group 1a, Cohorts 2, 3, and 4) or the commercial PZQ formulation (Treatment group 1b) at Day 1.

Blinding of site personnel and participants/parents is not warranted in this study, since the primary efficacy assessment of egg count using the Kato-Katz method is an objective laboratory measure. Laboratory personnel will remain blinded to a participant's treatment group and screening or baseline values. To minimize bias regarding the population of participants included for analysis of the primary efficacy outcome, the list of reasons for protocol violations will be finalized before final analysis of post treatment egg counts.

### **6.3.3 Emergency Unblinding**

Not applicable.

## **6.4 Study Intervention Compliance**

All study interventions will be administered as dispersible tablets dispersed in water (or dispersed in water after crushing of Biltricide tablets for Treatment group 1b) under the supervision of the Investigator or designee. The study intervention administration will be recorded in the electronic case report form (eCRF).

Study intervention administration records will be used to assess compliance.

The Investigator is responsible for the control of study interventions; adequate record of receipt (e.g., Drug Receipt Record) and disposition (e.g., Drug Accountability Record, Drug Destruction Record) of the study intervention including dates, quantities and use by the study participant must be maintained.

All records and study intervention supplies must be available for inspection at every monitoring visit. When the study is terminated and study intervention accountability has been satisfactorily

completed by the pharmacist/Investigator or study drug preparer (or designee), the used and unused study drug (i.e. empty, partially used and unused containers) should be destroyed at the clinical study site after written approval by the Sponsor. The completed Drug Accountability and Drug Destruction Records will be sent to the monitor or its designee.

The site pharmacist or pharmacist assistant must maintain records of the study intervention delivery to the study site, the inventory at the site, the use by each participant and its destruction or returning after study intervention accountability has been performed by the responsible monitor. The drug-dispensing log must be kept updated, listing the identification of the participant who received drug along with the date and quantity of drug dispensed; it must be available for monitoring. Temperature of the storage location will be monitored and documented.

The Investigator will ensure that the study intervention supply is not used for any purpose other than this study.

## **6.5 Concomitant Therapy**

All concomitant therapies (e.g., medicines or nondrug interventions) used from the time participant's parent or guardian/legally authorized representative signs the ICF until completion of the study, including any changes, will be recorded in the appropriate eCRF. For prescription and over-the-counter medicines, vaccines, vitamins, and herbal supplements, the name, reason for use, dates administered, and dosing information will be recorded. All concomitant medications (within 7 days of participant's study treatment) received by nursing mothers of enrolled participants will be recorded on the appropriate eCRF.

Contact the Medical Monitor for any questions on concomitant or prior therapy.

### **6.5.1 Rescue Medicine**

Biltricide may be administered to address ineffective Schistosomiasis treatment. Other rescue medications may be administered to treat anticipated adverse reactions or anticipated emergency reactions.

### **6.5.2 Permitted Medicines**

Any medicines that are considered necessary to protect the participant's welfare in emergencies may be given at the Investigator's discretion, regardless if it results in a protocol deviation.

### **6.5.3 Prohibited Medicines**

As referred to in the exclusion criteria (Section 5.2), administration of PZQ or use of any investigational device within 4 weeks prior to administration of the study intervention (PZQ ODT or Biltricide) and during the entire clinical study is not permitted.

If the administration of a non-permitted concomitant drug becomes necessary during the study, e.g., because of AEs, the participant should be discontinued from the study but only after consultation with the Sponsor. Children who require malaria treatment after receiving study treatment will not be withdrawn from the study, but because some anti-malarial agents (e.g.,

artemisinin derivatives) have activity against *Schistosoma* spp. (Liu et al, 2011), they will be excluded from the primary efficacy analysis.

For children being breastfed, administration of PZQ to nursing mothers is not allowed in the 3 days prior to PZQ ODT administration (see Section 6.5).

The concomitant administration of agents that induce the drug-metabolising enzyme system in the liver (cytochrome P450), such as certain antiepileptics (e.g., carbamazepine or phenytoin), glucocorticosteroids (e.g., dexamethasone) or chloroquine, may lead to reduced plasma levels of PZQ and will not be allowed. The concomitant administration of rifampicin, which is a strong inducer of cytochrome P450, or of other cytochrome P450 inducers, is contraindicated as no therapeutically effective plasma levels of PZQ can be expected in that setting.

Similarly, the concomitant administration of agents that inhibit the cytochrome P450 system, e.g., cimetidine, may lead to increased plasma levels and a prolonged retention period of PZQ and will not be allowed.

As consumption of grapefruit may lead to increased PZQ levels, grapefruits and grapefruit juice products will not be allowed during confinement. In case a participant may have been enrolled and dosed after grapefruit consumption, a protocol deviation will be issued, however participants will not be discontinued from the study and data won't be excluded from the analysis. The Investigator will need to enquire the eventual consumption of grapefruit in the 24 hours before enrolment and ensure that the child eats only the standard meals during confinement. At discharge, he will explain the parent/guardian/legally authorized representative the importance of abstaining from grapefruit consumption until 24 hours after the study intervention administration.

Also, any medication from screening until the End-of-Study visit is not allowed without prior approval from the Investigator (except for occasional use of paracetamol or ibuprofen). All medications that are administered from screening through the End-of-Study visit will be recorded on the appropriate eCRF.

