## 6.8

### Special Precautions

The medication administration part of the study will be conducted in a setting with access to basic emergency facilities. Equipment and other agents (epinephrine, prednisolone equivalents, etc.) will be made available at the study site in case of severe allergic reactions.

Participants will be observed when receiving the study intervention. They will remain in the facility for at least 12 hours after dosing and will be closely monitored.

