### 7.2 Participant Discontinuation/Withdrawal from the Study

This is a single-dose treatment study. If a participant withdraws prior to administration of the study treatment, the End-of-Study visit will be performed and no attempts will be made to collect additional data. No further evaluations will be performed, except for safety purpose when applicable.

- A participant may withdraw from the study at any time, upon request of participant's parent or guardian/legally authorized representative (i.e., withdrawal of consent) or if the child communicates (verbally or opposing resistance) that he/she is unwilling to continue, and without giving a reason. However, the reason should be obtained when it is possible to do so, and then the reason should be reported in the appropriate Case Report Form.
- The participant may be withdrawn by the Investigator due to participation in another clinical study.
- The participant may be withdrawn at any time at the discretion of the Investigator for safety, behavioral, compliance, or administrative reasons.
- The participant may be withdrawn if lost to follow-up.
- If a participant withdraws from the study, no further evaluations should be performed, and no attempts should be made to collect additional data, with the exception of safety data, which should still be collected if possible, but not captured in the database.
- If a participant is withdrawn from the study because of a treatment-limiting AE, thorough efforts should be made to clearly document the outcome.
- Data obtained prior to a participant's withdrawal will still be included in the efficacy and safety analysis.
- Participants withdrawn from the study will not be replaced.

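### The Section 6.5.3 discontinuation rule also covers children already given their single dose, where it limits no exposure and can lose scheduled outcome and safety data (rare, low priority)

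*Protocol*

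**What the plan says.** **The rule.** Protocol 6.5.3 states that when a non-permitted drug becomes necessary, "e.g., because of AEs, the participant should be discontinued from the study but only after consultation with the Sponsor". The sentence covers the whole study and does not mention whether the child has been dosed.

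**Its two exemptions.** The same section provides, for malaria: "Children who require malaria treatment after receiving study treatment will not be withdrawn from the study". Those children leave the primary efficacy analysis instead. For grapefruit taken before dosing, "a protocol deviation will be issued, however participants will not be discontinued from the study".

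**What may be given.** Section 6.5.1 adds to Biltricide: "Other rescue medications may be administered to treat anticipated adverse reactions or anticipated emergency reactions". Section 6.5.2 says medicines needed in an emergency "may be given at the Investigator's discretion, regardless if it results in a protocol deviation". Neither section says whether the child then stays in follow-up.

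**What leaving means.** Section 7.2: "If a participant withdraws from the study, no further evaluations should be performed, and no attempts should be made to collect additional data". Safety data are the exception, but they are kept outside the database. The follow-up part of Section 8 instead asks for an early final visit with the End-of-Study procedures.

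**The analysis.** Protocol 9.4.1 and SAP 14.1.1 treat a missing post-treatment result as not cured in the imputed mITT analysis. SAP 14.1.1 also plans the mITT table without imputation. SAP 8.1 lists, as an important deviation, a child who meets a withdrawal criterion but is not withdrawn. SAP 8.2 makes that a reason for exclusion from the PP set, and separately excludes users of prohibited medication.

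**The concern.** In a multi-dose trial, taking a patient off treatment because of an interacting drug protects the patient. Here there is one dose on Day 1, and Section 7.1 says discontinuation of study intervention does not apply. Once the dose is swallowed, the rule can only end observation.

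An adverse event and the drug used to treat it could then decide whose scheduled data are lost. A child who had just needed treatment for an event would drop out of the database for later safety findings. In the imputed mITT analysis the same child would count as a treatment failure, although the sample could have been collected. Section 6.5.3 avoids this for malaria treatment and grapefruit but not for other drugs. A team that sensibly kept a dosed child would risk having that recorded as an important deviation under SAP 8.1.

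**Working it through.** **Step 1. Does the rule do anything useful?**

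| Timing | Effect of discontinuing |
|---|---|
| Before dosing | Useful: a child on an enzyme inducer or inhibitor should not be dosed |
| After dosing, praziquantel given | Useful for the endpoint: the egg count no longer reflects the study dose |
| After dosing, other non-permitted drug | No exposure is left to limit; follow-up ends |

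**Step 2. What is lost, and what is not?**

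- Kept: the event itself, the 12-hour laboratory tests if already done, all data before withdrawal, the documented outcome of a treatment-limiting event, and follow-up of serious events (Protocol 7.2, 8, 8.3.3).
- At risk: the Day 17-21 egg counts, vital signs and physical examination; the database record of later non-serious events, which 8.3.1 otherwise captures up to End of Study; and the Day 35-40 urine samples in group 4b (the SAP's label for Cohort 4 at 60 mg/kg).
- The early exit visit in Section 8 sits badly with 7.2. It is also timed as soon as possible, so it does not secure samples inside the Day 17-21 window.

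**Step 3. Reproduce the plan's precision.** Inputs: 100 children in group 1a less 5% for malaria treatment gives 95 in mITT. For group 1b, 50 x 0.95 = 47.5, taken as 47. Both come from Protocol 9.2, Table 5. The Clopper-Pearson 95% interval for 76/95 = 80.0% is 70.5 to 87.5, which matches the stated lower bound of 70.5% and precision of 9.5 points. For group 4b, 43/57 = 75.4% has lower bound 62.2, a distance of 13.2 points, as the plan states for n = 57.

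**Step 4. Lose one child who would have been cured, before Day 17.** Under imputation the numerator falls by 1 and the denominator n is unchanged, so the shift is 1/n.

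| Group | Before | After | Shift |
|---|---|---|---|
| 1a | 76/95 = 80.0% (70.5 to 87.5) | 75/95 = 78.9% (69.4 to 86.6) | 1/95 = 1.05 points |
| 1b | 37/47 = 78.7% | 36/47 = 76.6% | 1/47 = 2.1 points |
| 4b, each visit | 43/57 = 75.4% (62.2 to 85.9) | 42/57 = 73.7% (60.3 to 84.5) | 1/57 = 1.75 points |

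In group 4b a missing Day 35-40 result takes the End-of-Study result (SAP 14.2). That result is itself imputed here, so both visits score as not cured. Without imputation, group 1a would read 75/94 = 79.8% (70.2 to 87.4). A child who would not have been cured changes nothing in the imputed cure rate. For the egg reduction rate, the same carry-forward rule enters a lost child as no change.

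**Step 5. How often?** The documents give no rate of non-permitted drug use for an adverse event, so the number of affected children is an assumption. In group 1a, 0, 1, 2 or 3 cured children lost give 80.0%, 78.9%, 77.9% or 76.8%. Protocol 2.3 reports no withdrawals due to adverse events in Phase II Part 1 (420 children randomized). That suggests rarity but does not measure use of barred drugs.

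**The case against.** **The obvious example mostly falls outside the rule.** Section 6.5.3 says of barred agents that "glucocorticosteroids (e.g., dexamethasone) or chloroquine, may lead to reduced plasma levels of PZQ and will not be allowed", while Section 6.8 says: "Equipment and other agents (epinephrine, prednisolone equivalents, etc.) will be made available at the study site in case of severe allergic reactions". A reader might infer that a child with a severe allergic reaction is refused a steroid, waits for the Sponsor before getting it, or must leave for having had it. The documents do not support that. Sections 6.5.1 and 6.5.2 permit rescue and emergency drugs, 6.5.2 names a protocol deviation as the possible consequence, and the Sponsor is consulted about discontinuation, not about treatment. What remains is mainly a barred drug, such as an antiepileptic or cimetidine, given after dosing for an event that is neither an emergency nor an anticipated reaction. This stands, and it narrows the point considerably.

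**The rule is discretionary.** It is worded as a recommendation and requires consultation, and the reasons listed in 7.2 do not name prohibited medication. This is true, but the default is still discontinuation, and SAP 8.1 and 8.2 penalise the alternative if the rule is read as a withdrawal criterion.

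**The SAP already expects such children.** SAP 12 lists prohibited concomitant drugs and SAP 8.2 removes their users from PP. A reader might infer that the SAP contradicts the protocol. It does not: both provisions fit a trial in which some children stay and others leave. Nor do they tell a site to keep the child.

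**A blanket exemption could inflate the cure rate.** If every drug except praziquantel were exempt after dosing, a child cleared by another anthelminthic would count as cured in mITT, whereas discontinuation with imputation scores that child as not cured. This objection is right, and the fix below allows for it.

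**Conclusion.** The point holds in a limited form. As written, 6.5.3 reaches children who have already had their only dose. Applied to them, it limits no exposure and can lose in-window outcome data and later safety data. Neither Sponsor consultation nor the early exit visit secures those data.

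The size is small: 1.05 points per cured child in group 1a against a planned precision of 9.5 points, 2.1 points in group 1b, and 1.75 points at each visit in group 4b. A reader might infer a material bias in the primary estimate. The documents do not support that: no hypothesis is tested, the arms are not compared statistically, and the planned table without imputation would show the effect.

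The conclusion assumes that the Sponsor applies the rule to a dosed child, that the child leaves before Day 17, that 7.2 rather than the exit-visit text governs, and that the child would have been cured. The number of such children is unknown and probably very small. This is a cheap, low-priority improvement.

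**What to change.** 1. In Protocol 6.5.3, limit the discontinuation rule to non-permitted drugs needed before dosing; such a child is not dosed.
2. State that a non-permitted drug given after dosing is recorded as a concomitant medication and a protocol deviation, and does not by itself end participation. Scheduled visits, samples and safety data, including Day 35-40 in group 4b, are still collected and entered in the database.
3. Keep the bar on praziquantel during the study. For any other drug with antischistosomal activity, such as another anthelminthic, keep the child in follow-up but do not count the egg result as a cure in the primary mITT analysis. Either exclude the child, as for antimalarials, or score the child as not cured, and choose between these in advance.
4. Cross-refer to this from 6.5.1 and 6.5.2.
5. In SAP 8.1 and 8.2, state that continued follow-up of such a child is not a failure to withdraw. The PP exclusion for prohibited medication stays.

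No change is needed to which drugs may be given, to how an adverse event is treated, or to how 7.2 handles other withdrawals.

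**Cost.** A few protocol sentences, two cross-references and a short SAP addition covering items 3 and 5. No visit or sample is added. The downside is that a few mITT outcomes will follow a concomitant drug; the PP analysis, which excludes those children, can show whether that matters.
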